	medical causes of symptoms and to describe change in symptom scores after addressing those causes identified. To determine the
	feasibility of the IBD symptom checklist and algorithm in clinical
	practice and the costs incurred by the NHS, and additional
	qualitative process evaluation.
Number of	200 patients
Participants/Patients	
Main Inclusion	Inclusion criteria
Criteria	 Diagnosis of IBD (including patients with an ileo-anal pouch or stoma)
	18 years and over
	Lives in UK and attends one of the IBD-BOOST clinical
	sites for routine IBD care
	 Has completed the IBD-BOOST survey (stage 2 of
	Programme Grant) and indicated that they would like further support to help manage their symptoms
	Ability to give informed consent and sufficient command of
	English to understand study documents and procedures will be assumed from response to the previous survey
	Exclusion criteria
L	

	Under 18 years	
Analysis	 Statistical analysis to determine: Proportion of patients with at least one potentially treatable cause for symptom/s (including active IBD disease flare-up). For those receiving any test or intervention for a potentially treatable cause identified by the algorithm: change in symptom scores for fatigue, pain and incontinence will be estimated (at 3 months). Proportion of people completing the checklist who have symptoms but subsequently decline suggested medical test or intervention (such as a blood test or medication). Health economics analysis to estimate (among participants undergoing medical optimisation): IBD-related healthcare use and costs incurred for tests and subsequent interventions (NHS perspective) Change in health-related quality of life (EQ-5D-5L utility) Qualitative analysis of process evaluation interviews with staff members (1 per site) carrying out the study for insights on feasibility and suggested modifications. 	
Proposed Start Date	1 st June 2019	
Proposed End Date	31 st December 2022	
Proposed follow-up end	31 st March 2023	
Study Recruitment Duration	43 months	
Study Total duration	46 months	

ROLES AND RESPONSIBILITIES OF COMMITEES/GROUPS & INDIVIDUALS

The Chief Investigator (CI) ([name]) has overall responsibility for the study.

The Programme Management Group (PMG), includes all co-investigators of the IBD-BOOST programme as well as the research team. The PMG and research team are responsible for the planning, execution, analysis and writing up the project.

Programme Co-investigators

[name]	Queen Mary University of London

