If nothing further needs to be done according to the algorithm (patient is in remission and no further tests or management is indicated), the participant will be informed of this, thanked for their participation by letter/email (Appendix 14). They will be offered the RCT if they have consented for further research contact and are eligible for the RCT. If active IBD disease or any other of the issues in the IBD-BOOST algorithm are identified, the IBD nurse/clinician will initiate management based on the algorithm.

If a participant is clinically unwell, with a plan to change their IBD management at the time of their checklist being reviewed, their study participation should be paused. The participant should be informed of this pause in their participation via email/letter (Appendix 15) and a new checklist should be re-sent to them 6 months later via post or email. This new checklist should then be used to follow the algorithm. Participants will also complete a new faecal calprotectin sample at the same time as completing the new checklist.

Participants will have completed measures of symptom severity and IBD control when completing the checklist. If intervention is indicted by the algorithm, they will complete the patient reported outcome questionnaire (Appendix 6) at 3 months after return of both the checklist and faecal calprotectin test (only for those for whom the checklist indicates an abnormality which the algorithm addresses). Nurses will keep a record of their interactions with patients (phone calls, emails or clinic visits), tests ordered, results and interventions using a case report form (Appendix 5).

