6. DATA COLLECTION

The checklist (Appendix 4) and outcome measures at 3 months (Appendix 6) will be selfadministered. Participants will be invited to complete these through an online link provided or via paper copies sent to the study research team and stored at King's College London or LNWUH Trust. Data from the online version will be directly inputted into the database by participants. Paper copies received in the post will be inputted manually into the database by the research team.

Results for calprotectin tests on stool samples provided by the participant will be accessed by the central research team on King's College Hospital laboratory's secure results portal and uploaded on to the study database on the Calprotectin CRF (Appendix 11). Once the checklist and algorithm data are both available the participant's usual care clinical site will have four weeks to review and contact the participant.

If the checklist indicates an abnormality which the algorithm addresses, the participant will be sent the patient reported outcomes questionnaire (Appendix 6) at 3 months after the IBD nurse has reviewed the checklist. The questionnaire contains measures on symptom and IBD control repeated from the checklist and measures of quality of life also used in the IBD-

BOOST survey. Those who require a 3 month follow up will be sent this via email/letter and will be sent up to 2 reminders by email or text message for non-responders (Appendix 10).

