6.2 Outcome measures

Primary outcome measures

Proportion of participants with any of the following detected via the checklist, faecal calprotectin test or by the nurse/clinician following the algorithm (recorded on the Checklist, Appendix 4 & Optimisation CRF, Appendix 5):

- "Red flags" on checklist which require investigation
- Active disease (defined as faecal calprotectin 200 or over and/or IBD control score 13 or under)
- Abnormalities detected on blood test in people with fatigue
- Irritable Bowel Syndrome or functional dyspepsia diagnosed in people with pain (by responses on checklist)
- Untreated loose stool detected in people with urgency

Secondary outcomes

- Proportion of participants for whom a clinical intervention was indicated
- Proportion of participants who declined a suggested clinical intervention at consultation
- The cost of implementing the algorithm (clinical tests or intervention and nurse/clinician time to implement the algorithm)
 The checklist (Appendix 4) also includes the following measures, which will be repeated at 3 months (Appendix 6):

- PROMIS Short Form v1.0 Fatigue 4a; 4 item validated scale to measure fatigue (14)
- PROMIS Scale v1.0 Pain Intensity 3a; 3 item validated scale to measure pain (14)
- PROMIS Scale v1.0 Gastrointestinal Bowel Incontinence 4a; 4 item validated scale to measure bowel control (15)
- IBD-Control score; 8-item self-reported score to measure disease control from the patient's perspective (13)
- EQ-5D-5L (Quality of Life measurement); a 5-item standardised measure of health (16)

Only those participants needing interventions as indicated by the algorithm, will be sent the outcome questionnaire (Appendix 6) at 3 months after return of the initial checklist and stool sample. This questionnaire will also include a free text feedback option at follow up to capture qualitative comments about the experience of completing the checklist and algorithm, and how onerous or helpful this was.

In addition, the nurse/clinician will complete the Optimisation CRF for each participant (Appendix 5), this will include number of visits or telephone contacts, all tests and results and all management initiated within the algorithm. Qualitative comments on taking the participant through the process of using the checklist and algorithm will be collected here.

Feasibility outcomes will include number consenting but then discontinuing (with reasons if possible), completion of outcome measures, completion of CRFs.

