6.3 IBD-BOOST Study Schedule

IBD-BOOST OPTIMISE		Within 1 week of completing checklist	Within 10 weeks of consent/ 2 weeks of trial team receiving the calprotectin result	Within 4 weeks of checklist and calprotectin data sent to clinical team	Within 3 months of checklist and calprotectin result reviewed	3 months after checklist and calprotectin result reviewed	Before study closure
Time Point	Т0	T1	T2	Т3	T4	T5	T6
Screening and invite sent	Х						
Participant Information Sheet	Х						
Consent Form	Х						
Checklist	Х						
Stool sample kit sent to participant		Х					
Calprotectin result received and uploaded by central research team			X				
Checklist and calprotectin result reviewed by patient's local IBD team				Х			
Medical Management Optimisation (if required)					X		
Participant reported Outcome Questionnaire completed (only if management provided)						X	
Clinician Qualitative Process Evaluation Interviews							Х

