7. DATA ANALYSIS, MANAGEMENT AND PROTECTION

7.1 Data analysis

The percentage of patients requesting help with their symptoms who report at least one treatable cause will be estimated. The percentage of patients with each treatable cause will be estimated among all those seeking help. For those receiving intervention, change in fatigue, pain and incontinence scores will be estimated with confidence intervals.

The change in generic health-related quality of life (EQ-5D-5L) from survey to end of optimisation and the cost of implementing the optimisation algorithm will be evaluated.

We will collect data on all significant health (NHS perspective) resource inputs associated with optimising medical management. This will include hospital visits, diagnostic procedures, medication. The intervention-specific cost (email, telephone contacts, and tests) will be calculated based on the records (by nurses and doctors) of their interactions with patients. Unit costs from national sources will be applied to estimate patient-level total healthcare costs.

Free text comments from participants gathered in the questionnaire at 3 months (Appendix 6) and from nurses/clinicians (Appendix 5) will be subjected to a simple thematic analysis to determine views on feasibility and any changes suggested.

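### The protocol gives three different rules for who receives the 3-month questionnaire and two different analysis sets for symptom change

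*Protocol*

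**What the plan says.** **Who gets the form.** The protocol answers this in four places.

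- Section 6 (Data collection): "If the checklist indicates an abnormality which the algorithm addresses, the participant will be sent the patient reported outcomes questionnaire".
- Section 3 (Study design) has a main clause, "If intervention is indicted by the algorithm, they will complete the patient reported outcome questionnaire" (the verb is evidently a misprint for indicated), and then a bracket that restricts it: "only for those for whom the checklist indicates an abnormality which the algorithm addresses".
- Section 6.2 (Outcome measures): "Only those participants needing interventions as indicated by the algorithm, will be sent the outcome questionnaire".
- Section 6.3 (Study schedule) marks completion of the form as "only if management provided".

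**Who is analysed.** The study summary defines the symptom-change analysis with "For those receiving any test or intervention for a potentially treatable cause identified by the algorithm". Section 7.1 says "For those receiving intervention, change in fatigue, pain and incontinence scores will be estimated with confidence intervals".

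**What the analysis must answer.** Secondary question II in section 2.2 concerns patients with symptoms and a potentially reversible cause, and asks whether the symptoms change by 3 months after algorithm-led management begins. Question IV asks about EQ-5D-5L utility in patients starting that management.

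**The concern.** The trigger for the questionnaire is an instruction for data collection. If a participant is not sent the form, the 3-month fatigue, pain, incontinence, IBD-Control and EQ-5D-5L data do not exist, and no analysis plan can restore them. Questions II and IV both rest on this one form.

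The loss would also be selective. The checklist rule would leave out people whose treatable cause came to light only through a laboratory result or the clinician's review. The schedule rule would leave out people who were tested but not treated, and people who declined. The protocol expects decliners and counts them as a secondary outcome.

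With two analysis sets stated, the denominator of the reported change is also open.

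**Working it through.** **The protocol's own figure.** The only precision figure is in section 4.3, a 95% interval at most 13.9% wide for the primary proportion. It reproduces: 2 × 1.96 × √(0.5 × 0.5 / 200) = 0.1386. It does not concern the questionnaire, and no figure is given for the follow-up set. The check is therefore a comparison of texts.

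**Is the checklist a separate source from calprotectin?** Yes.

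- Section 6.2 lists three routes of detection for the primary outcome: the checklist, the calprotectin test, and the nurse or clinician following the algorithm.
- Section 3 sends the stool kit only after the checklist has been returned.
- Section 6 places the result on its own form, the Calprotectin CRF.
- Section 6.2 defines active disease as calprotectin of 200 or over and/or an IBD-Control score of 13 or under, so calprotectin alone is enough.

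A participant with a clear checklist and raised calprotectin therefore meets the primary outcome.

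**Applying each rule to each kind of participant.**

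| Participant | Sent: section 6, bracket in 3 | Sent: section 6.2, main clause of 3 | Sent: section 6.3 | Analysed: summary | Analysed: section 7.1 |
|---|---|---|---|---|---|
| Checklist abnormality, managed | yes | yes | yes | yes | yes |
| Calprotectin 200 or over only, managed | **no** | yes | yes | yes | yes |
| Found only by clinician or blood test, managed | **no**, unless reporting the symptom itself counts as a checklist abnormality | yes | yes | yes | yes |
| Checklist abnormality, tested, no management started | yes | depends on whether a test is an intervention | **no** | yes | unclear |
| Intervention indicated but declined | if checklist-positive | yes | **no** | only if a test was done | no |

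Only the first row is treated the same way throughout. Rows two and three can be in both analysis sets and have no data. Row four is analysed under the summary, but the schedule collects nothing from it. Row five is sent the form under section 6.2 but not under section 6.3.

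**Size, by assumption only.** The protocol gives neither the share with a treatable cause nor the share of those found by calprotectin alone. Number omitted under the literal checklist rule = 200 × share with a cause × share found by calprotectin alone.

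- 30% and 5%: 200 × 0.30 × 0.05 = 3.
- 50% and 20%: 200 × 0.50 × 0.20 = 20 of 100.
- 70% and 30%: 200 × 0.70 × 0.30 = 42 of 140.

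These rates show the spread; they are not estimates.

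**The case against.** **The checklist wording may be loose drafting.** The main clause of section 3 agrees with section 6.2. Section 3 also calls calprotectin a step in the algorithm, and section 6.3 times the form from review of both the checklist and the calprotectin result. On that reading a calprotectin-only participant gets the form. A reader might infer that such people will certainly have no follow-up. The documents do not support that, because it happens only if section 6, or the bracket in section 3, is followed over section 6.2. But nothing says which takes precedence, so the risk stands.

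**Intervention may include tests.** The summary speaks of declining a test or an intervention, with a blood test as an example, while section 6.2 calls the matching outcome declining a clinical intervention. Section 7.1 could be shorthand for the set in the summary. Section 1.4, however, distinguishes tests from new management. This part is an ambiguity rather than a plain contradiction.

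**Pooling across symptoms.** A reader might infer that section 7.1 dilutes each score change by including people without that symptom. The documents do not establish this. Section 7.1 is a one-sentence outline, and the population for each scale is commonly left to the statistical analysis plan, which is not shown. No figure in the protocol supports an amount of dilution. Limiting each estimate to people with the symptom at the checklist also has a price: it selects on the baseline measurement, and in an uncontrolled before-after study regression to the mean would then inflate the apparent improvement.

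**The stakes are modest.** Symptom change is a secondary, descriptive outcome in a study now focused on feasibility, and section 2.2 disclaims causal inference. The primary outcome does not depend on the questionnaire. This stands, and it limits how serious the point is.

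**Conclusion.** The point holds for the definitions. There are three incompatible triggers for the 3-month form, two of them within one sentence of section 3, and two statements of the analysis set. Followed literally, the checklist trigger leaves people found only by calprotectin, clinician or blood test without 3-month symptom or EQ-5D-5L data, although they meet the primary outcome and section 6.2 would include them. The schedule trigger leaves out tested-only participants whom the summary analyses, and decliners to whom section 6.2 would send the form.

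The number lost cannot be derived from the documents; it depends on which rule sites and the central team apply and on rates the protocol does not give. The passages should be reconciled because data not collected cannot be recovered and the correction is cheap.

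**What to change.** 1. **One trigger, worded identically in sections 3, 6, 6.2 and 6.3.** Send the form to every participant for whom the algorithm indicates action (a test or management) through any of the three routes: checklist, calprotectin or clinician.
2. **One analysis set, stated in both the summary and section 7.1.** To match question II, use those who started algorithm-led management as recorded on the Optimisation CRF.
3. **Separate reporting.** Give tested-only and declining participants their own descriptive results. Flag any who have entered the RCT, since section 1.1 allows it to be offered to decliners.
4. **Optional.** Estimates by baseline symptom may stand beside the all-treated estimate as a supplementary description, with a note on regression to the mean. They need not be the main estimate.

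The cost is protocol wording, an adjusted rule for sending out the form, and a few more questionnaires.

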6.2 Outcome measures

Primary outcome measures

Proportion of participants with any of the following detected via the checklist, faecal calprotectin test or by the nurse/clinician following the algorithm (recorded on the Checklist, Appendix 4 & Optimisation CRF, Appendix 5):

- "Red flags" on checklist which require investigation
- Active disease (defined as faecal calprotectin 200 or over and/or IBD control score 13 or under)
- Abnormalities detected on blood test in people with fatigue
- Irritable Bowel Syndrome or functional dyspepsia diagnosed in people with pain (by responses on checklist)
- Untreated loose stool detected in people with urgency

Secondary outcomes

- Proportion of participants for whom a clinical intervention was indicated
- Proportion of participants who declined a suggested clinical intervention at consultation
- The cost of implementing the algorithm (clinical tests or intervention and nurse/clinician time to implement the algorithm)
 The checklist (Appendix 4) also includes the following measures, which will be repeated at 3 months (Appendix 6):

- PROMIS Short Form v1.0 Fatigue 4a; 4 item validated scale to measure fatigue (14)
- PROMIS Scale v1.0 Pain Intensity 3a; 3 item validated scale to measure pain (14)
- PROMIS Scale v1.0 Gastrointestinal Bowel Incontinence 4a; 4 item validated scale to measure bowel control (15)
- IBD-Control score; 8-item self-reported score to measure disease control from the patient's perspective (13)
- EQ-5D-5L (Quality of Life measurement); a 5-item standardised measure of health (16)

Only those participants needing interventions as indicated by the algorithm, will be sent the outcome questionnaire (Appendix 6) at 3 months after return of the initial checklist and stool sample. This questionnaire will also include a free text feedback option at follow up to capture qualitative comments about the experience of completing the checklist and algorithm, and how onerous or helpful this was.

In addition, the nurse/clinician will complete the Optimisation CRF for each participant (Appendix 5), this will include number of visits or telephone contacts, all tests and results and all management initiated within the algorithm. Qualitative comments on taking the participant through the process of using the checklist and algorithm will be collected here.

Feasibility outcomes will include number consenting but then discontinuing (with reasons if possible), completion of outcome measures, completion of CRFs.

Process evaluation interviews

Due to having a reduced overall sample size (from 500 to 200 participants), a result of the impact of the Covid-19 pandemic on recruitment, the study will now focus on intervention feasibility. In order to try to establish whether implementing this checklist and algorithm would be feasible in routine NHS clinical practice, and what factors impact this, we will conduct telephone or Teams/Skype interviews with NHS clinicians (1 per site) who worked on the IBD-BOOST Optimise study.

Interviews will be completed to understand experiences of the using the checklist and algorithm, their acceptability, which aspects were most or least helpful, and the feasibility of implementing their use in routine NHS clinical practice, as well as any suggestions for improvements/changes.

Staff members working on the study will be contacted by the central team using the information leaflet (Appendix 16). Those indicating willingness will be interviewed using a topic guide (Appendix 17). The data will be analysed iteratively and as the interviews progress the topic guide will be adapted, based on themes which emerge from earlier interviews, to enable exploration of issues which appear relevant in later interviews.

All interviewees will be read the consent form questions by the interviewer (telephone or Teams/Skype interviews) and agreement to each statement will be audio recorded. Appendix 18 gives the consent form for NHS staff interviews.

Analysis: Interpretive data analysis will be informed by the Analytical Hierarchy Framework (AHF) (17), guiding methods for handling, analysing and generating findings from qualitative

data. This generic framework is appropriate for exploratory qualitative work as it guides the process of analysis through basic organisational data management stages, to descriptive and finally interpretive levels. The AHF acts as a set of instructions for progression through analysis; the specific detailed method of analysis is achieved through simultaneous use of a specific coding frame as part of that process.

Early findings will be collated, with new items identified in the first-round analysis being added to the coding frame. The research team will then conduct a second analysis using the enhanced coding frame. This iterative process can be repeated as required to ensure a thorough and robust analysis of the data. NVivo software will be used to manage data and enable sorting, labelling and retrieval of data segments prior to the human endeavour of interpretation and representation of findings.

